### **On-site Monitoring**

Member networks that accrue less than five patients per year will not be monitored on site, unless other deficiencies have been identified, and thus indicate the need for a monitoring visit. Member networks that accrue five or more patients will be monitored approximately every 12 months. Member networks that accrue 10 or more patients per year will be monitored approximately every 6 months.

The first on-site monitoring visit will occur after the fifth patient has been enrolled and within 6 months after the fifth patient enrollment. Thereafter, on-site monitoring visits will occur at approximately 12-month intervals during the treatment phase of the study.

At the end of each on-site monitoring visit, the monitor will debrief the site study team and highlight areas that need improvement (if applicable). Any actions or findings will be documented in a visit follow-up letter, and on-site monitoring visit follow-up letters will be distributed to the Site Principal Investigator and Lead Clinical Research Professional within 4 weeks (30 days) of the last day of the on-site monitoring visit, but no later than 6 weeks (42 days).

All affiliate/component sites will be monitored at the main member site during scheduled on-site visits, unless a separate on-site visit is deemed necessary. All records from affiliate/component sites must be accessible to monitors.

Routine monitoring visits will be scheduled at approximately 6-12-month intervals, depending on accrual and other KPIs to ensure proper oversight of trial execution. On-site monitoring visits will only be conducted during the treatment phase. Central data monitoring will continue and sites will be audited per the Alliance auditing schedule during the follow-up phase.

Frequency of monitoring visits may be adjusted and will be determined based upon factors such as enrollment rate, data quality, protocol compliance, site performance, and the available amount of data to be monitored.

Inadequate attention to the protection of rights and safety of human patients, unreported or underreported safety information, or other non-compliance may result in an increase in the percentage of patient data monitored or monitoring visit frequency.

At selected sites, a minimum of 25% of patients will be selected for on-site SDV of the following:

- Primary endpoint
- Secondary endpoints

At selected sites, a minimum of 25% of patients will be selected for on-site SDV of the following:

- Eligibility

At selected sites, 100% of patients will be selected for on-site SDV of the following:

- Informed consent
- Expedited adverse events/serious adverse events
- Treatment administration
- Patient termination

On-site audits will be conducted according to the NCI Clinical Trials Monitoring Branch guidelines.

On-site monitoring will be conducted according to Alliance procedures.

### **13.7 Descriptive Factors**

- Number of Lymph Nodes Resected and Examined:  $\geq 12$  vs.  $< 12$
- Tumor Characteristics, Perforation: Yes vs. No
- Tumor Characteristics, Obstruction: Yes vs. No
- Tumor Characteristics, Adherence: Yes vs. No

**13.8 Inclusion of Women and Minorities**

DOMESTIC PLANNED ENROLLMENT REPORT					
Racial Categories	Ethnic Categories				Total
	Not Hispanic or Latino		Hispanic or Latino		
	Female	Male	Female	Male	
American Indian/ Alaska Native	2	2	1	1	6
Asian	21	22	2	1	46
Native Hawaiian or Other Pacific Islander	3	3	1	1	8
Black or African American	21	22	2	1	46
White	272	276	19	15	582
More Than One Race	5	5	1	1	12
Total	324	330	26	20	700

**14.0 CORRELATIVE SCIENCE COMPANION STUDIES****14.1 Quality of Life Study in Alliance A021502: A021502-HO1****14.1.1 Background**

Quality of life has been demonstrated to be a key outcome in colorectal cancer. We previously studied the quality of life of patients receiving mFOLFOX6 with or without cetuximab in the N0147 clinical trial (paper under review). Quality of life was measured using Linear Analog Self-Assessment (LASA) items measuring overall quality of life, physical well-being, mental well-being, and fatigue prior to randomization, after 6 cycles of treatment, and at end of treatment. The study concluded no disease-free survival benefits to adding cetuximab to adjuvant mFOLFOX6. In 1,422 patients completing questionnaires, patients receiving mFOLFOX6 with cetuximab reported significantly worse overall quality of life (3 points on a 0-100 scale,  $p=0.01$ ), mental well-being (3 points on a 0-100 scale,  $p=0.05$ ), and physical well-being (2 points on a 0-100 scale) at end of treatment than those patients who also received mFOLFOX6 alone. These results were consistent across sex and KRAS subgroups. Patients aged over 70 appeared to start and end the study with higher mental well-being (baseline: 4 points on a 0-100 scale,  $p=0.0001$ ; end of treatment: 3 points on a 0-100 scale,  $p=0.03$ ) than patients aged  $<70$ . However, the 70+ age group also started and ended the trial with higher levels of fatigue (baseline: 7 points on a 0-100 scale,  $p=0.01$ ; end of treatment: 6 points on a 0-100 scale,  $p=0.08$ ) than the  $<70$  age group, though cetuximab did not appear to impact fatigue in either age group. These data support inclusion of elderly patients for studies in this population. Long-term quality of life was not assessed in this study.

There is also emerging data suggesting that immunotherapy could potentially reduce oxaliplatin-related peripheral neuropathy [46]. However, there are anecdotal reports that immune checkpoint inhibitors can cause polyneuropathy and most would regard this as a greater concern. Oxaliplatin typically causes a toxic neuropathy that may not have a major immune component. So the effect of atezolizumab on neuropathy when given in combination with mFOLFOX6 is unknown at this time (i.e. whether neuropathy will be non-inferior or perhaps even superior on the combination arm compared to mFOLFOX6 alone).

In addition, reported studies have not assessed the impact of atezolizumab using patient-reported outcomes. The purpose of this correlative study is to assess the impact of atezolizumab (both short-term during treatment as well as long-term at the 3-year post-registration time point) on patient-reported neuropathy, overall quality of life, and functioning. We will also assess health utilities and quality adjusted life years (QALYs) to fulfill Genentech requirements, and to combine PROs with overall survival data to complement the efficacy findings of the main protocol. Additionally, we intend to further investigate a methodological question about the relationship between both from side effects and newly developed PRO-CTCAE items which are collected within the standard adverse event reporting of the main protocol.

#### 14.1.2 Objectives

Primary: Compare peripheral neuropathy during the first six months of the study as assessed by the FACT/GOG-NTX (NTX subscale score – sensory items) between patients randomized to mFOLFOX6 + atezolizumab vs. mFOLFOX6. We hypothesize that patient-reported neuropathy will be non-inferior in the mFOLFOX6 + atezolizumab arm compared to the mFOLFOX6 arm.

Secondary: Compare health-related quality of life (HRQL) during the first six months of the study as assessed by the FACT-C Trial Outcome Index (TOI) between patients randomized to mFOLFOX6 + atezolizumab vs. mFOLFOX6. We hypothesize that HRQL will be non-inferior in the mFOLFOX6 + atezolizumab arm compared to the mFOLFOX6 arm.

Exploratory: Compare health utilities during the first six months of the study as assessed by the EQ-5D-5L between patients randomized to mFOLFOX6 + atezolizumab vs. mFOLFOX6. We hypothesize that the health utilities will be non-inferior in the mFOLFOX6 + atezolizumab arm compared to the mFOLFOX6 arm.

Exploratory: Compare patient-reported neuropathy and HRQL at the 3-year long-term follow-up between patients randomized to mFOLFOX6 + atezolizumab vs. mFOLFOX6. We hypothesize that patient-reported neuropathy and HRQL of the mFOLFOX6 + atezolizumab arm will be non-inferior to that of the mFOLFOX6 alone arm.

Exploratory: Explore the relationship between patient-reported symptom bother using the single item from the FACT-C “I am bothered by side effects of treatment” and patient-reported symptomatic toxicity profile as measured by PRO-CTCAE (which is collected within the standard adverse event reporting of the main protocol).

#### 14.1.3 Methods

The FACT-C quality of life questionnaire will be used to assess the quality of life of patients randomized to each treatment arm [12]. This questionnaire is comprised of 38 validated questions that can be used in assessing quality of life in the study population. The FACT-C will be completed by consented patients at registration and approximately 3 months, 6 months, 12 months, and 3 years after registration. Patient-reported neuropathy will also be assessed using the 11 additional questions of the FACT/GOG-NTX [47]. EQ-5D-5L is a short, 6-question, instrument which assesses a patient’s overall quality of life or health state [48]. The addition of the EQ-5D-5L will allow for

computation and comparison between arms of health utilities and QALYs and is needed in the current protocol to satisfy European Union reimbursement agency requirements.

For information regarding ordering and administering booklets, see [Section 4.3](#) and [Section 6.4](#). Booklets will be administered at the following time points in Arm 1: at registration, prior to treatment on Cycles 4, 7, and 13, at end of treatment, and 3 years after registration. In Arm 2, time points were designed to match those of Arm 1, though require post-treatment time points since treatment is only 6 months in duration on this arm. Thus time points in Arm 2 include: at registration, prior to treatment on cycles 4 and 7, at end of treatment, 12 months, and 3 years after registration. The booklet contains 55 questions and it is anticipated that the booklet will take approximately 10-15 minutes for the patient to complete at each administration time point. We anticipate having booklets available in English and Spanish. Patients who consent to participate in this quality of life study (A021502-HO1) may decline to complete a booklet at any time. The primary reason for each missed booklet will be collected on a case report form.

#### 14.1.4 Statistical Considerations

All questionnaires will be scored according to published scoring algorithms. The primary analysis over the first six months of treatment will involve a single mixed model for the primary endpoint of FACT/GOG-NTX NTX sensory neuropathy subscale score (sum of NTX1-4). A mixed model will compare time points up to the 1 year time point between randomized arms. In addition to a randomized arm covariate, the model will include a randomized arm-by-time interaction term and will use the planned cycle of assessment as the categorical time value. Unstructured covariance will initially be used, though alternative covariance structures will be investigated with the final covariance structure selected based on minimization of the Akaike information criterion. A contrast will be used to compare mean change from baseline at 6 months between arms. If the two-sided 95% confidence interval excludes a difference of 1.9 endpoints (on the 0-16 point NTX sensory neuropathy scale) favoring the mFOLFOX6 arm, then non-inferiority will be concluded. The difference of 1.9 points represents 0.5 standard deviations, or a clinically meaningful effect based on the work of Normal et al [49], using the pooled standard deviation (computed as 3.8 points) of the sensory neuropathy scale as reported at the end of treatment in Cella et al [50]. For the secondary endpoint of HRQOL (measured by the FACT-C TOI), a similar analysis will be undertaken with a non-inferiority cutoff of 6 points (which is the minimally important difference for the FACT-C TOI [51] favoring mFOLFOX6. Group differences and confidence intervals will also be constructed using standard effect sizes (i.e. differences in terms of standard deviation units) to aid in interpretation. Supplemental analysis will include similar non-inferiority analyses for other scales of the FACT/GOG-NTX and FACT-C, including the constituent scales of the TOI, using published minimally important differences and/or standard effect sizes (i.e. 0.5 standard deviations) as cutoffs for non-inferiority at 6 months, and will include comparison of the mean changes from baseline at each of the remaining post-baseline time points. The change from 6 months to 1 year will also be compared between arms. In preliminary analyses, baseline patient characteristics will be compared between arms using t-tests for continuous variables and chi-squared tests for categorical variables in the cohort of patients who are evaluable for the primary analysis of this substudy. In the event that meaningful imbalances or other confounding factors are identified, supplemental analyses to the primary and secondary analyses will

incorporate baseline patient characteristics or other confounding factors as covariates in mixed models.

Primary patient-reported outcome analysis will be conducted at the time that all consented patients have completed the 1-year assessment visit (or are no longer being followed for QOL). The analysis of the 3-year time point will occur at the time that all consented patients have completed the 3-year assessment visit (or are no longer being followed for QOL). Timing of release of the data for presentation will be at the discretion of the DSMB. Patients will be analyzed according to the randomized treatment arm assignment. All randomized patients who consent for participation in the PRO component with a baseline endpoint value and at least one endpoint value post-registration will be included in the analysis for a given endpoint. In the primary analysis, all observations available will be used. See below for information regarding analyses to account for missing data.

Exploratory analysis will include similar mixed model comparisons of change from baseline in EQ-5D-5L health utility scores at 6 months with a non-inferiority margin of 0.06 points [52]. Patient QALYs will be computed using the area-under-the-curve approach (with and without discounting) and will include all data through the follow-up of the last consented patient (i.e. the earliest censored patient). A population-based approach will also be used such that the area-under-the-curve of a quality-adjusted survival curve (mean health utility multiplied by the proportion of patients surviving based on Kaplan-Meier estimates) is the mean quality-adjusted survival for the population. Mean quality-adjusted survival will then be compared between arms using a bootstrap approach. Exploratory analysis will also include comparison of the mean changes from baseline at the 3-year time point using a contrast from a mixed model (similar to the primary analysis, however including data through the 3-year time point). Finally, exploratory methodological analysis will include regression analyses at fixed time points to assess the relationship between patient-reported bother and PRO-CTCAE symptom profiles. The goal is to investigate what drives symptom bother – individual symptoms (e.g. worst symptom score) or cumulative symptom experience (e.g. average symptom score). Potential PRO-CTCAE cut-points may also be explored. Graphical procedures throughout analysis will include plots of average values over time by arm for each primary, secondary, and exploratory endpoint.

For all statistical analyses, two-sided 95% confidence intervals will be used (p-values <0.05 will be considered statistically significant for hypothesis testing). For interpreting the clinical significance of effects, 0.2, 0.5, and 0.8 standard deviation (SD) effects will be considered as small, moderate, and large based on Cohen [53] throughout. Minimally important differences for the FACT-C will also be used [51].

Missing data will be handled in a number of ways. Missing items within a summary or scale score will be handled according to each questionnaire's published scoring algorithms. Missing data at the summary or scale score level will be handled as follows. Baseline patient/disease characteristics will be compared between patients who do and do not provide data for the primary analysis. We will also graphically explore patterns of missing data. All analyses will be completed using all available data, followed by analyses completed using a range of imputation methods. Lastly, we will employ pattern mixture models for longitudinal analyses. Output from all analyses will be

tabulated and descriptively compared to assess the degree to which missing data impacts study results.

**Power:** Assuming that 490 patients are evaluable for the primary analysis (i.e. allowing up to 30% of patients to decline consent or be non-evaluable for the primary analysis), this QOL study has 91% power to exclude a 1.9 point difference (a moderate and clinically meaningful 0.5 standard deviation difference) in patient-reported neuropathy between arms using a two-sided  $\alpha=0.05$  test, assuming that the pooled standard deviation is 3.8 points and the true difference between the arms is 0.76 points (a small 0.2 standard deviation difference) favoring mFOLFOX6. If the true difference between arms is 0 points, this sample size would have 90% power to exclude a 1.14 point difference (a small to moderate 0.3 standard deviation difference) in patient-reported neuropathy between arms using a two-sided  $\alpha=0.05$  test, again assuming that the pooled standard deviation is 3.8 points. The secondary analysis has 98% power, if the true difference in HRQOL between arms is 2.12 points (a small 0.2 standard deviation difference) favoring mFOLFOX6 assuming that the non-inferiority margin of 6 points represents a 0.56 standard deviation difference (i.e. assuming the FACT-C TOI scale has a standard deviation of 10.6) [54].

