### Pre-Study Testing Intervals

- To be completed < 28 DAYS before registration: Laboratory studies, history and physical; dMMR testing may be completed at any point prior to registration for the present tumor.
- To be completed ≤ 80 DAYS before registration: Any imaging used to confirm lack of evidence of definitive metastatic disease (pre-surgery scans are acceptable)

	Prior to Registration*	Arm 1: Day 1 of each cycle*	Arm 2: Day 1 of each cycle*	End of treatment follow-up**	Post-treatment follow-up ***
Tests & Observations					
History and Physical, Weight, PS	A	A	A	X	X
Height	X	X(1)	X(1)	X(1)	
Pulse, Blood Pressure	X	X	X	X	
O 2 Saturation	X(2)	X(2)		X(2)	
CTCAE Adverse Event Assessment		X(3)	X(3)	X(3)	X(3)
PRO-CTCAE Adverse Event Assessment	X(4)	X(4)	X(4)	X(4)	
Registration Fatigue/ Uniscale Assessment	X(5)				
Colonoscopy	B				B
Tanner Staging	X(1)	C(1)	C(1)	X(1)	X (1)
Laboratory Studies					
Complete Blood Count, incl. Diff.	X	X	X	X	
Chemistry	X(6)	X(6)	X(6)	X(6)	
TSH	X(7)	X(7)			
Hep B Surface Ag & Hep C ab (Physician Discretion)	X				
Serum or Urine HCG	X(8)				
CEA	X(9)	X(9)	X(9)		X(9)
CD4 Count & Viral Load	X(10)				
dMMR Testing	X				
Staging					
CT of Chest/Abd/Pelvis or MRI of Chest/Abd/Pelvis	D	E	E	E	E
Correlative Studies: For patients who consent to participate					
QOL Assessments	Arm 1: At registration, prior to Cycles 4, 7, and 13, at the end of treatment, and 3 years from registration. Arm 2: At registration, prior to Cycles 4 and 7, at the end of treatment, 12 months from registration, and 3 years from registration. See Sections 6.4, 14.1, and Appendix I .				

Tissue, Blood, and Stool Samples	See Sections 6.2 and 14.2 .
----------------------------------	---

\* Labs and visits completed prior to registration may be used for Day 1 of Cycle 1 (or Day 1 of Cycle 2) tests if obtained  $\leq 14$  days prior to treatment. For subsequent cycles, labs and visits may be obtained  $\leq 2$  business days prior to day of treatment.

\*\* Physical examination, adverse event assessment, labs (CBC and chemistry), and staging scans (if due per footnote D) are required 1 month (+/- 7 days) after the last day of the last treatment cycle.

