### 3.1.3 End of Treatment (EoT)

EoT visit should be conducted 1 month (+/- 7 days) after the last day of the last treatment cycle. The following procedures will be performed during the EoT visit:

Mandatory procedures all arms:		
Procedure	Instruction	pCRF
Vital signs	Blood pressure	

	Heart rate	
Oxygen saturation	Oxygen saturation should be assessed at rest after 1 minute walk.	
Weight, BSA		
Full physical examination	incl. general appearance, skin, lymph nodes, respiratory, cardiovascular, abdominal, head and neck (including ears, eyes, nose and throat), musculo-skeletal (including spine and extremities), genital/rectal, neurological and thyroid function	
Cardiac function tests	QT interval monitoring acc. to local standards	Y
Pregnancy test	Serum HCG or high sensitivity urine HCG for WOCBP	Y
ECOG Performance Status		
Hematology	Hematocrit Hemoglobin Red blood cell count Platelet count Lymphocytes Basophils Eosinophils Monocytes Neutrophils Total white cell count	Y
Chemistry	Total protein Albumin Alkaline phosphatase Alanine aminotransferase Aspartate aminotransferase Bicarbonate Calcium Chloride Serum Creatinine Glucose Potassium Sodium Magnesium Total bilirubin Blood urea nitrogen	Y
Colonoscopy	Patients who did not receive a colonoscopy to the cecum prior to surgery are required to	

	have a full colonoscopy no later than 6 weeks after the completion of chemotherapy, but exact timing within the specified window is per treating physician discretion.	
Toxicities/ adverse events	Document using NCI-CTCAE v5.0	
Patient-reported outcomes	NCI PRO-CTCAE™	

Mandatory procedures all arms - Every 6 months (+/- 1 month) for the first 2 years after registration:		
Procedure	Instruction	pCRF
Radiologic tumor assessment	The same imaging modality used at baseline must be used for all subsequent scans.	Y

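### The 6-month neuropathy contrast in the QOL substudy compares Arm 1 about 14 days, and Arm 2 about 43 days, after the last oxaliplatin dose

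*Combined protocol and SAP*

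**What the plan says.** The primary analysis of substudy A021502-HO1 (14.1.4) is a mixed model for the sensory neuropathy score with arm, time and arm-by-time terms. It "will use the planned cycle of assessment as the categorical time value". The test is a single comparison from that model: "A contrast will be used to compare mean change from baseline at 6 months between arms". Non-inferiority is concluded on this rule: "If the two-sided 95% confidence interval excludes a difference of 1.9 endpoints", in the direction favoring mFOLFOX6.

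The booklet schedule is in the Study Calendar (5.0) and is repeated in 6.4 and 14.1.3. The calendar's entry for the atezolizumab arm reads: "Arm 1: At registration, prior to Cycles 4, 7, and 13, at the end of treatment, and 3 years from registration". The control arm's entry drops the Cycle 13 booklet and adds one at a year: "Arm 2: At registration, prior to Cycles 4 and 7, at the end of treatment, 12 months from registration, and 3 years from registration".

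The booklet windows are in 6.4: 3 days either side for the pre-cycle booklets and 7 days either side for the End of Treatment Visit. The AIO appendix (3.1.3) says when that visit takes place: "EoT visit should be conducted 1 month (+/- 7 days) after the last day of the last treatment cycle". The footnote to the Study Calendar gives the same timing.

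Section 14.1.3 states the intention: "In Arm 2, time points were designed to match those of Arm 1". The same sentence adds that Arm 2 needs post-treatment time points because its treatment lasts only 6 months. No section says which booklet supplies Arm 2's 6-month value.

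**The concern.** Arm 2 has no Cycle 13. Its only booklet between Cycle 7 and 12 months is the one at the End of Treatment Visit, so that booklet must be its 6-month value. Arm 1's 6-month value comes from the booklet before Cycle 13. With planned labels as categorical time, the two are treated as simultaneous although one comes weeks later relative to the last oxaliplatin dose.

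That matters for this endpoint. The neuropathy items in Appendix I ask about the past 7 days, and 10.4 describes oxaliplatin neurotoxicity as lessening in 82% of patients by 4 to 6 months. Any change over the extra weeks in Arm 2 enters the contrast as if it were a treatment effect.

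Early stopping adds a second asymmetry. An Arm 2 patient who stops early still completes an End of Treatment booklet, which planned labelling would count as 6 months. An Arm 1 patient who stops all treatment early has no pre-Cycle 13 booklet, and in that arm the end-of-treatment label belongs to about month 12.

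**Working it through.** **Timing, for patients on schedule.** Inputs: 14-day cycles (7.0); oxaliplatin on Day 1 of each cycle, last planned dose at Cycle 12 in both arms (7.1, 7.2); booklet windows (6.4); End of Treatment Visit timing (5.0; AIO appendix 3.1.3). One month is taken as 30 days, and Cycle 1 Day 1 is day 0.

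| | Arm 1 (pre-Cycle 13) | Arm 2 (End of Treatment Visit) |
|---|---|---|
| Last oxaliplatin | 11 × 14 = day 154 | day 154 |
| Booklet | 12 × 14 = day 168 | 154 + 13 + 30 = day 197 |
| Days since oxaliplatin | 14 | 43 |
| Window | 11 to 17 | 36 to 50 |

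The gap is 197 − 168 = 29 days, and the windows do not overlap. If the last day of the cycle is read as the last drug day (Day 3), Arm 2 is at 2 + 30 = 32 days (25 to 39). The gap is then 18 days, still without overlap.

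**Early stoppers.** Take an Arm 2 patient whose last cycle is Cycle 5. The last day of that cycle is 5 × 14 − 1 = day 69, so the End of Treatment booklet falls at about day 99. Planned labelling would place it with values collected near day 197.

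**The plan's power figure.** Inputs from 14.1.4: 490 evaluable patients (245 per arm at 1:1), margin 1.9, two-sided alpha 0.05, "assuming that the pooled standard deviation is 3.8 points and the true difference between the arms is 0.76 points" favoring mFOLFOX6.

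- SE = 3.8 × √(2/245) = 0.343
- Power = Φ((1.9 − 0.76)/0.343 − 1.96) = 0.913

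This reproduces the stated 91%, which assumes no timing difference.

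**Effect of a drift.** Let b be the number of points by which Arm 2 looks better because of its later booklet. The documents give no value for b, so the values below are assumptions. Power = Φ((1.9 − true difference − b)/0.343 − 1.96).

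| b (points) | True difference 0.76 | True difference 0 |
|---|---|---|
| 0 | 91% | above 99% |
| 0.25 | 74% | 99.8% |
| 0.5 | 46% | 98% |

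On the plan's SD, 0.25 points is 0.25/3.8 = 0.07 SD.

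**The case against.** Several objections have force.

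- **Mapping.** The visit footnote in the Study Calendar does not list QOL booklets. The link rests on the visit name in 6.4, which is the only visit so defined. The inference is reasonable, but it remains an inference.
- **Disclosure.** Section 14.1.3 admits that the schedules differ and calls its times approximate. It does not acknowledge a gap at the primary time point.
- **Size.** Section 10.4 covers 4 to 6 months and gives no change in points over four weeks. The power loss also depends on the assumed true difference of 0.76: with no true difference, the test keeps about 98% power or more at the same drifts.
- **Existing safeguards.** Contrasts at the other time points are already planned, including the matched pre-Cycle 4 and pre-Cycle 7 booklets, and so are imputation and pattern-mixture analyses. None of these corrects the primary contrast. The supplemental covariate models in 14.1.4 cannot do so either: for on-schedule patients, days since oxaliplatin is almost the same variable as arm.

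Two stronger readings are tempting, and the documents do not support them. A reader might infer that the offset could produce a false claim of non-inferiority. That would need neuropathy to worsen in the weeks after stopping, which no section describes; 10.4 points the other way. A reader might also infer that Arm 1's 6-month data come only from patients still on full treatment. Under 8.2, a patient who drops one drug continues the others, so an Arm 1 patient off oxaliplatin but on atezolizumab still reaches Cycle 13. Only those who stop all treatment lack that booklet, and their other booklets still enter the model.

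**Conclusion.** The concern holds in this limited form. At the primary PRO time point, on-schedule patients are compared about 14 versus about 43 days after the last oxaliplatin dose, and the planned time variable hides the 29-day gap. Early stoppers are also labelled differently by arm.

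The size of the bias is unknown. Its likelier direction, from 10.4, is against concluding non-inferiority, so the practical risk is a failed or attenuated result that cannot be attributed to atezolizumab rather than to visit timing. The conclusion assumes treatment on schedule through Cycle 12, and that Arm 2's End of Treatment booklet is its 6-month value.

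This should be fixed. It is confined to the QOL substudy, where it also touches the 6-month FACT-C TOI and EQ-5D-5L contrasts and the 6-month-to-1-year change. DFS and OS are not affected.

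**What to change.** Amend 14.1.4 before the arm comparison is seen:

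1. State which booklet supplies the 6-month value in each arm.
2. Assign each booklet by its actual date, so that an early stopper's End of Treatment booklet is not counted as 6 months.
3. Fit the mixed model with actual time from registration and take the arm contrast at one prespecified day common to both arms. State that the result depends on the time model: at day 168, for example, Arm 2 is interpolated between its pre-Cycle 7 booklet (6 × 14 = day 84) and about day 197.
4. Report the matched pre-Cycle 4 and pre-Cycle 7 contrasts beside it as supporting evidence.
5. Apply the same rules to the TOI and EQ-5D-5L contrasts and to the 6-month-to-1-year change.

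A wide visit window around 6 months would not close the gap, because days 168 and 197 would both fall inside it. A matched Arm 2 booklet would close it, but is probably too late, at least in Germany, where the AIO appendix (1.5) planned the last treatment for February 2023.

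The cost is SAP wording, programming with data already collected, and a slightly wider interval.

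### The QOL non-inferiority test compares unadjusted change from baseline, which is usually less precise than a baseline-adjusted contrast, and its 91% power rests on an SD that is not the SD of change

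*Combined protocol and SAP*

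**What the plan says.** All of this is in section 14.1.4.

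- **Model.** "the model will include a randomized arm-by-time interaction term and will use the planned cycle of assessment as the categorical time value". On covariance: "Unstructured covariance will initially be used, though alternative covariance structures will be investigated", with the final structure chosen by AIC. No term for the baseline score and no common baseline mean is named.
- **Test.** "A contrast will be used to compare mean change from baseline at 6 months between arms". The decision rule begins "If the two-sided 95% confidence interval excludes a difference of 1.9 endpoints" on the 0-16 scale, in the direction favouring mFOLFOX6.
- **Covariates.** If meaningful imbalance or confounding is found, supplemental analyses will "incorporate baseline patient characteristics or other confounding factors as covariates in mixed models". The primary model does not depend on this.
- **Power.** "this QOL study has 91% power to exclude a 1.9 point difference" with 490 evaluable patients, "assuming that the pooled standard deviation is 3.8 points and the true difference between the arms is 0.76 points" in favour of mFOLFOX6. The 3.8 is described as the SD of the scale at the end of treatment in a cited trial.
- **Analysis set.** A patient needs a baseline value and at least one later value to be included.
- **Other scales.** FACT-C TOI and EQ-5D-5L utilities get similar analyses.

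Section 2.3 mentions adjusting for baseline QOL and fatigue, but for the efficacy of atezolizumab, not for this model.

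**The concern.** With separate baseline means by arm, the 6-month contrast in change is a difference of change scores. A change score uses the baseline with its coefficient fixed at 1. A baseline-adjusted contrast estimates that coefficient and removes whatever variance the baseline can explain. The confidence interval alone decides non-inferiority, so a needlessly wide interval raises the chance of missing the 1.9-point margin when the treatment is in fact non-inferior.

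The power statement also describes a different quantity from the one tested. It uses the spread of scores at one time point, whereas the test is on change, whose spread depends on the baseline SD and on the correlation between baseline and 6 months. Neither is stated, so a reader cannot tell whether 91% is too high or too low for the planned test.

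**Working it through.** **Inputs from section 14.1.4:** 490 evaluable, taken as 245 per arm (1:1 allocation, section 13.0); margin 1.9; true difference 0.76; SD 3.8; two-sided 95% interval. The distance to the margin is 1.9 − 0.76 = 1.14 points.

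**Assumed, because the documents do not give them:** baseline SD s0 (3.8 or 2.0) and baseline-to-6-month correlation ρ (0.2 to 0.6). The 6-month SD s6 is held at the plan's 3.8.

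**1. Reproduce the stated power.** The standard error is 3.8 × √(2/245) = 0.343, and 1.14/0.343 = 3.32. Power = Φ(3.32 − 1.96) = 91.3%, matching the stated 91%. The calculation is a two-sample comparison of scores with SD 3.8.

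**2. Variances of the two contrasts, per patient.**

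- Planned (change): s0² + s6² − 2ρ·s0·s6
- Baseline-adjusted: s6²(1 − ρ²)
- Difference: (s0 − ρ·s6)², which is never negative and is zero only when s0 = ρ·s6

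A generalised least squares check with four visits, complete data, equal SDs of 3.8 and equal correlations agrees. At ρ = 0.3 the planned arm-by-time contrast has standard error 0.406, which is the change-score value. Constraining the baseline means to be equal gives 0.328, which is the adjusted value.

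**3. Power = Φ(1.14 / (SD × √(2/245)) − 1.96).**

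| Assumed baseline SD | ρ | SD of change | Planned power | Adjusted SD | Adjusted power |
|---|---|---|---|---|---|
| 3.8 | 0.2 | 4.81 | 74.7% | 3.72 | 92.3% |
| 3.8 | 0.3 | 4.50 | 80.1% | 3.62 | 93.6% |
| 3.8 | 0.5 | 3.80 | 91.3% | 3.29 | 97.0% |
| 3.8 | 0.6 | 3.40 | 96.0% | 3.04 | 98.6% |
| 2.0 | 0.2 | 3.92 | 89.5% | 3.72 | 92.3% |
| 2.0 | 0.3 | 3.73 | 92.3% | 3.62 | 93.6% |
| 2.0 | 0.5 | 3.29 | 96.9% | 3.29 | 97.0% |

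**4. Break-even.** The planned contrast has the stated power when the SD of change equals 3.8, that is when ρ = s0/(2 × 3.8). This is 0.50 for a baseline SD of 3.8 and 2.0/7.6 = 0.26 for a baseline SD of 2.0. Below that correlation power falls short of 91%; above it, power exceeds 91%.

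**5. FACT-C TOI.** The plan's inputs (SD 10.6, margin 6, true difference 2.12) reproduce its 98% (98.2%). If the baseline SD is also 10.6 and ρ = 0.3, both assumed, the SD of change is 10.6 × √1.4 = 12.5. Planned power is then about 93%, against about 99% adjusted.

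**The case against.** The strongest reply is that the NTX baseline is probably narrow. Section 3.2.8 excludes grade 2 or higher peripheral neuropathy, and section 3.2.3 allows at most one earlier cycle of mFOLFOX6. Scores at registration should then sit near the symptom-free end. With a baseline SD of 2.0 the gain is at most about 3 points of power over ρ = 0.2 to 0.5, and the plan reaches 91% from ρ of about 0.26. This stands, and it limits the size of the point for NTX. It does not remove the point. Grade 1 neuropathy and one oxaliplatin cycle are allowed, low correlations still cost power, and a neuropathy exclusion says little about the spread of the TOI at baseline.

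It is also fair to say that a change-from-baseline contrast is a common prespecified choice in an optional substudy, away from DFS and OS.

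A reader might infer more than the documents support:

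- **That the substudy is underpowered.** The 91% is correct on its own inputs, and without a baseline SD or correlation the true figure could lie on either side.
- **That the test is biased, or that chance baseline imbalance passes straight into the estimate.** Randomisation protects the contrast. What remains of an imbalance is the fraction (ρ·s6/s0 − 1). At s0 = 2.0 and ρ = 0.5 that is 0.95 − 1, or 5% in size. Full carry-over needs ρ = 0.
- **That the imbalance tests choose the primary model.** They lead only to supplemental analyses.

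**Conclusion.** The point holds as one of efficiency and documentation. The planned contrast leaves available precision unused, by (s0 − ρ·s6)² in per-patient variance, and the SD behind its power statement is not the SD of the quantity tested. The size depends on two figures that the plan does not state. At ρ = 0.3 the gain from adjustment is 13.5 points of power (80.1% to 93.6%) with a baseline SD of 3.8, and 1.3 points (92.3% to 93.6%) with a baseline SD of 2.0. A shortfall below 91% is possible, not demonstrated.

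The adjusted contrast has at least 91% power at any correlation only if the 6-month SD really is 3.8 and 490 patients are evaluable. With a 6-month SD of 4.2, for example, adjusted power is 87% at ρ = 0.2. These are large-sample results with complete data; missing visits would change the figures.

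**What to change.** In the primary mixed model for NTX, and likewise for FACT-C TOI and EQ-5D-5L, constrain the baseline means to be equal across arms, or add the baseline score and baseline-by-time as covariates. Including the section 4.6 stratification factors is optional; nothing in the documents shows that they predict neuropathy.

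For power, either state the SD of change (or the baseline SD and correlation) behind the 91%, or base the statement on the adjusted contrast and name the 6-month SD of 3.8 as its condition. The imbalance-triggered supplemental models can stay as they are.

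The cost is SAP wording. The baseline score is already collected and already required for inclusion, so no patient is lost and no new data are needed.
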